8.3.2 Axillary Temperature Measurement

Pre-vaccination axillary temperature will be measured at Visit 1 and at subsequent study vaccination visits. Axillary is the only acceptable method of obtaining participant's temperature in the study.

If the participant has a fever within the 24-hour period prior to vaccination, the vaccination should be rescheduled as soon as possible after the fever has resolved. For the purpose of this study, a fever is defined as an axillary temperature $\geq 37.5^{\circ}\text{C}$ (or equivalent), in accordance with the local routine medical practice and China Regulatory Agency's Guideline for Grading Scales of Adverse Events in Clinical Trials of Prophylactic Vaccines (see Section 10.7 - Appendix 7: China-specific Requirements).

See Section 8.11.2 for other prerequisites for vaccination visit.

8.3.3 30-Minute Post-Vaccination Observation

All participants will be observed for at least 30 minutes after each study vaccination for any immediate untoward effects with particular attention to any evidence of allergic phenomena. This observation period will be documented in the participant's study chart.

8.3.4 Vaccination Report Card

VRC will be provided to each participant's legally acceptable representative at each study vaccination visit.

Participant's legally acceptable representative will be instructed to record the following information:

- Daily axillary temperature from Day 1 through Day 7 following each study vaccination (Temperature measurement must be recorded on the VRC if a fever is suspected during Day 8 through Day 30 [concomitant-use group] or Day 8 through Day 15 [staggered-use group]);
- Solicited injection-site AEs (erythema, swelling, induration, and pain at the injection-site of IPV) from Day 1 through Day 7 following each vaccination of IPV;
- Solicited systemic AEs (diarrhea and/or vomiting) from Day 1 through Day 7 following each study vaccination;
- Any AEs from Day 1 through Day 30 (concomitant-use group) or from Day 1 through Day 15 (staggered-use group) following each study vaccination;
- Any concomitant medications from Day 1 through Day 15 following each study vaccination (both vaccination groups).
- Any non-study vaccinations from Day 1 through Day 30 (concomitant-use group) or from Day 1 through Day 15 (staggered-use group) following each study vaccination;
- Any medications due to AE during Day 16 through Day 30 following each study vaccination (concomitant-use group only).

Although Visit 1 is not a vaccination visit for participants in the concomitant-use group, VRC will be provided to each participant's legally acceptable representative to record any reportable safety events from randomization through the first study vaccination (See Section 8.4.1 for safety reporting requirement).

At least one telephone contact will be conducted by investigator within 7 days after each visit of VRC distribution to remind each participant's legally acceptable representative to record the VRC and answer their any questions related to VRC.

In the concomitant-use group, the purpose of Visit 3, 5, and 7 is only to review VRCs, so out of windows of these visits will not be reported as a protocol deviation in this vaccination group.

8.3.5 Clinical Safety Laboratory Assessments

1. There are no protocol specified laboratory assessments in this study.
 - If laboratory values from nonprotocol-specified laboratory assessments performed at the institution's local laboratory require a change in study participant management or are considered clinically significant by the investigator (eg, SAE or AE or dose modification), then the results must be recorded in the appropriate CRF (eg, SLAB).

8.4 Adverse Events, Serious Adverse Events, and Other Reportable Safety Events

The definitions of an AE or SAE, as well as the method of recording, evaluating, and assessing causality of AE and SAE and the procedures for completing and transmitting AE, SAE, and other reportable safety event reports can be found in Appendix 3.

Adverse events, SAEs, and other reportable safety events will be reported by the participant (or, when appropriate, by a caregiver, surrogate, or the participant's legally authorized representative).

The investigator and any designees are responsible for detecting, documenting, and reporting events that meet the definition of an AE or SAE as well as other reportable safety events. Investigators remain responsible for following up AEs, SAEs, and other reportable safety events for outcome according to Section 8.4.3.

The investigator, who is a qualified physician, will assess events that meet the definition of an AE or SAE as well as other reportable safety events with respect to seriousness, intensity/toxicity and causality.

8.4.1 Time Period and Frequency for Collecting AE, SAE, and Other Reportable Safety Event Information

All AEs, SAEs, and other reportable safety events that occur after the consent form is signed but before randomization/allocation must be reported by the investigator if they cause the participant to be excluded from the study, or are the result of a protocol-specified intervention, including but not limited to washout or discontinuation of usual therapy, diet, placebo, or a procedure.

From the time of randomization/allocation through 30 days (concomitant-use group) or 15 days (staggered-use group) following the first vaccination(s) and from the time of any subsequent vaccination(s) through 30 days (concomitant-use group) or 15 days (staggered-use group) thereafter, all AEs, SAEs, and other reportable safety events must be reported by the investigator.

Additionally, SAE (regardless of causality) and intussusception (ECI) at any time outside of the time period specified in the previous paragraph also must be reported immediately to the Sponsor. Other reportable safety events (cancer and overdose) at any time outside of the time period specified in the previous paragraph should also be reported to the Sponsor.

Investigators are not obligated to actively seek AEs or SAEs or other reportable safety events in former study participants. However, if the investigator learns of any SAE, including a death, at any time after a participant has been discharged from the study, and he/she considers the event to be reasonably related to the study intervention or study participation, the investigator must promptly notify the Sponsor.

All initial and follow-up AEs, SAEs, and other reportable safety events will be recorded and reported to the Sponsor or designee within the time frames as indicated in [Table 2](#).

Table 2 Reporting Time Periods and Time Frames for Adverse Events and Other Reportable Safety Events

Type of Event	Reporting Time Period: Consent to Randomization/ Allocation	Reporting Time Period: Randomization/ Allocation through Protocol-specified Follow-up Period	Reporting Time Period: After the Protocol- specified Follow-up Period	Time Frame to Report Event and Follow-up Information to Sponsor:
Nonserious Adverse Event (NSAE)	Report if: - due to protocol-specified intervention - causes exclusion - participant is receiving placebo run-in or other run-in treatment	Report all	Not required	Per data entry guidelines
Serious Adverse Event (SAE)	Report if: - due to protocol-specified intervention - causes exclusion - participant is receiving placebo run-in or other run-in treatment	Report all	Report all (Follow ongoing to outcome)	Within 24 hours of learning of event
Event of Clinical Interest (require regulatory reporting)	Report if: - due to intervention - causes exclusion	Report all	Report all	Within 24 hours of learning of event
Cancer	Report if: - due to intervention - causes exclusion	Report all	Report all	Within 5 calendar days of learning of event
Overdose	Report if: - receiving placebo run-in or other run-in medication	Report all	Report all	Within 5 calendar days of learning of event

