1.3 Schedule of Activities

Visit Number		1	2	3	4	5	6	7	8	Notes
Study Month		Day 1	Month 0.5	Month 1	Month 1.5	Month 2	Month 2.5	Month 3	Month 3.5	
Recommended Age (Months)		~1.5	~2	~2.5	~3	~3.5	~4	~4.5	~5	
Concomitant-Use Group	Scheduled Day	Day 1	15 days after V1	15 days after V2	30 days after V2	15 days after V4	30 days after V4	15 days after V6	30 days after V6	
	Visit Window	48-63 days of age	15-21d after V1 (≤84 days of age)	15-21d after V2	30-42d after V2	15-21d after V4	30-42d after V4	15-21d after V6	30-42d after V6	
Staggered-Use Group	Scheduled Day	Day 1	15 days after V1	30 days after V1	30 days after V2	30 days after V3	30 days after V4	30 days after V5	30 days after V6	
	Visit Window	48-63 days of age	15-21d after V1	30-42d after V1 & ≥V2+15d	30-42d after V2 & ≥V3+15d	30-42d after V3 & ≥V4 +15d	30-42d after V4 & ≥V5+15d	30-42d after V5	30-42d after V6	
Administrative Procedures										
Informed Consent		X								Screening procedures may not be performed on the same day of ICF, but screening or rescreening visit should be on the same day as randomization. Screening procedures may be repeated after consultation with the Sponsor.
Assignment of Screening Number		X								
Participant Identification Card		X								
Inclusion/Exclusion Criteria		X								
Medical History		X								
Prior/Concomitant Medications Review		X	X	X	X	X	X	X	X	

Visit Number		1	2	3	4	5	6	7	8	Notes
Study Month		Day 1	Month 0.5	Month 1	Month 1.5	Month 2	Month 2.5	Month 3	Month 3.5	
Recommended Age (Months)		~1.5	~2	~2.5	~3	~3.5	~4	~4.5	~5	
Concomitant-Use Group	Scheduled Day	Day 1	15 days after V1	15 days after V2	30 days after V2	15 days after V4	30 days after V4	15 days after V6	30 days after V6	
	Visit Window	48-63 days of age	15-21d after V1 (≤84 days of age)	15-21d after V2	30-42d after V2	15-21d after V4	30-42d after V4	15-21d after V6	30-42d after V6	
Staggered-Use Group	Scheduled Day	Day 1	15 days after V1	30 days after V1	30 days after V2	30 days after V3	30 days after V4	30 days after V5	30 days after V6	
	Visit Window	48-63 days of age	15-21d after V1	30-42d after V1 & ≥V2+15d	30-42d after V2 & ≥V3+15d	30-42d after V3 & ≥V4+15d	30-42d after V4 & ≥V5+15d	30-42d after V5	30-42d after V6	
Assignment of Treatment/Randomization Number		X								The treatment/randomization number will be randomly assigned by an interactive response technology (IRT) system.

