4.2.1.2 Safety Endpoints

In the concomitant-use group, V260 and IPV will be administered on the same day with an interval of at least 30 days between each vaccination visit, and the safety of the two study vaccines will be collected for 30 days following each vaccination. In the staggered-use group, V260 and IPV will be administered separately with an interval of at least 15 days, therefore the safety of each study vaccine will be collected for 15 days following each vaccination.

Paper VRC will be provided to each participant's legally acceptable representative at each vaccination visit to record participant's daily axillary temperature from Day 1 through Day 7 post each study vaccination; solicited injection-site AEs (erythema, swelling, induration, and pain at the injection-site of IPV) from Day 1 through Day 7 post each vaccination of IPV, and solicited systemic AEs (diarrhea and/or vomiting) from Day 1 through Day 7 post each study vaccination; and any other AEs from Day 1 through Day 15 post study each vaccination in both the concomitant-use and staggered-use groups. In addition, any other AEs from Day 16 through Day 30 post each study vaccination in the concomitant-use group will also be collected on the VRC.

The solicited injection-site AEs will be collected for the safety evaluation of IPV, which is a vaccine to be intramuscularly administered.

Although participants in the concomitant-use group will not receive any study vaccines at Visit 1, VRC will be provided to each participant at Visit 1 to record any reportable safety events from randomization through the first study vaccination (See Section 8.4.1 for safety reporting requirement).

In addition, any SAEs regardless of causality, cancer, overdose, and intussusception (ECI) will be collected during the entire period of study.

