9.4.2 Safety Endpoints

A description of safety measures is presented in Section 4.2.1.2 and Section 8.3. The analysis of safety results is described in Section 9.6.2.

Safety and tolerability will be assessed by clinical review of all relevant parameters including AEs and post-vaccination temperature measurements following V260 and/or IPV.

The safety analysis endpoints include:

- Proportions of participants with solicited injection-site AEs (erythema, swelling, induration, and pain at the injection-site of IPV) from Day 1 through Day 7 post-vaccination of IPV in the two vaccination groups
- Proportions of participants with solicited systemic AEs (diarrhea and/or vomiting) from Day 1 through Day 7 post-vaccination of V260 and IPV in the concomitant-use group, and from Day 1 through Day 7 post-vaccination of V260 plus from Day 1 through Day 7 post-vaccination of IPV in the staggered-use group
- Proportions of participants with any injection-site AEs from Day 1 through Day 15 post-vaccination of V260 and IPV in the concomitant-use group, and from Day 1 through Day 15 post-vaccination of IPV in the staggered-use group
- Proportions of participants with any systemic AEs from Day 1 through Day 30 post-vaccination of V260 and IPV in the concomitant-use group, and from Day 1 through Day 15 post-vaccination of V260 plus from Day 1 through Day 15 post-vaccination of IPV in the staggered-use group
- Proportions of participants with any vaccine-related injection-site AEs from Day 1 through Day 15 post-vaccination of V260 and IPV in the concomitant-use group, and from Day 1 through Day 15 post-vaccination of IPV in the staggered-use group
- Proportions of participants with any vaccine-related systemic AEs from Day 1 through Day 30 post-vaccination of V260 and IPV in the concomitant-use group, and from Day 1 through Day 15 post-vaccination of V260 plus from Day 1 through Day 15 post-vaccination of IPV in the staggered-use group
- Proportion of participants with any SAE, any AE which is both vaccine-related and serious, any AE resulting in discontinuation, and proportion of participants who died, proportion of participants with intussusception during the entire study period in the two vaccination groups

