Any Vaccine-related Injection-Site AEs	Days 1-15 post-vaccination of V260 and IPV in the concomitant-use group, and Days 1-15 post-vaccination of IPV in the staggered-use group, across all dose periods and by dose period	X
Any Vaccine-related Systemic AEs	Days 1-30 post-vaccination of V260 and IPV in the concomitant-use group, and Days 1-15 post-vaccination of V260 plus Days 1-15 post-vaccination of IPV in the staggered-use group, across all dose periods and by dose period	X
Discontinuation due to any AE	Entire Study Period by Vaccination Group	X
Any Serious AEs including Intussusception	Entire Study Period by Vaccination Group	X

X = results will be provided.

To assess the severity of adverse events, both Sponsor's criteria (see "Assessment of Intensity/Toxicity" in Section 10.3 - Appendix 3) and China Regulatory Agency's criteria (see Section 10.7 - Appendix 7: Country-specific Requirements) will be applied. The incidence of greatest adverse event severity reported by a participant based on both the two criteria will be tabulated for: all injection-site AEs and all systemic AEs across all dose periods.

For the across dose-period summaries and analyses, if the same AE occurs multiple times across dose periods, the AE will be counted once. In order to evaluate any additive safety issues for the concomitant use of V260 and IPV compared to the staggered use of these vaccines, the following summaries will also be provided: Frequencies and percentages of the solicited systemic AEs during Days 1 to 7 after V260 concomitant with IPV in the concomitant-use group, during Days 1 to 7 after V260 alone in the staggered-use group, and during Days 1 to 7 after IPV alone in the staggered-use group.

Any injection-site AEs and vaccine-related injection-site AEs during Days 1 to 30 post-vaccination of V260 and IPV in the concomitant-use group will be summarized separately.

Any reportable safety events collected between Visit 1 and 2 in the concomitant-use group will be listed separately.

For serious adverse events observed during the study, including intussusception, a detailed description will be included in the CSR.

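### AE-related discontinuation is summarised over the whole study, but a nonserious AE starting outside the post-dose window need not be reported even if it stops vaccination, so the endpoint may be incomplete when visits run late

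*Combined protocol and SAP*

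**What the plan says.** The endpoint. Section 9.4.2 lists, for both groups, "any AE resulting in discontinuation, and proportion of participants who died, proportion of participants with intussusception during the entire study period". Table 5 in Section 9.6.2 repeats it as "Discontinuation due to any AE" and gives the entire study as its time period.

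The collection rule. Section 8.4.1 covers the time from randomization to the end of the first post-dose window. For each later vaccination it applies "through 30 days (concomitant-use group) or 15 days (staggered-use group) thereafter, all AEs, SAEs, and other reportable safety events must be reported by the investigator". Outside those windows it adds two groups of events. The first sentence begins "Additionally, SAE (regardless of causality) and intussusception (ECI) at any time outside of the time period specified"; the second reads "Other reportable safety events (cancer and overdose) at any time outside of the time period specified in the previous paragraph should also be reported". Neither mentions a nonserious AE that leads to discontinuation. Table 2 marks nonserious AEs after the protocol-specified follow-up as not required. The Synopsis describes follow-up after each vaccination as 30 days (concomitant) or 15 days (staggered), and the report card in Section 8.3.4 stops collecting AEs at the same days.

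The reason for the windows. Section 4.2.1.2 ties them to the minimum dosing intervals. For the staggered group, "V260 and IPV will be administered separately with an interval of at least 15 days", and AE collection is set at 15 days to match.

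The visit windows. Section 1.3 lets doses fall later than the minimum. The staggered Visit 3 window, for example, is "30-42d after V1 & ≥V2+15d".

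**The concern.** The endpoint claims a longer period than the rule that supplies its data. Section 7.1 lets vaccination be stopped for an untoward effect or a medical condition at any time, but the duty to report a nonserious AE lapses between doses whenever the next dose comes later than the minimum interval.

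The protocol already makes reporting depend on consequence in one place: before randomization, Section 8.4.1 requires an AE to be reported if it causes exclusion. It has no matching trigger after randomization for an AE that stops vaccination.

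At stake is the completeness of one tolerability summary. The disposition display in Section 9.6.3 could give an AE as the reason for stopping while the AE data hold no record of its onset, grade or causality.

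**Working it through.** **Inputs.** The visit windows come from Section 1.3 and the AE windows from Section 8.4.1. Visit 1 is day 0. The dose day counts as Day 1 of a window of 15 or 30 days, as on the report card. Uncovered days between consecutive doses = max(0, interval − window). If the dose day were counted as day 0, each non-zero gap would be one day shorter.

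**The plan's own figure.** On schedule, Visit 8 falls at day 105, and 105/30 = 3.5 months, which matches the stated duration of participation.

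**On the scheduled dates.**
- Staggered doses fall on days 0, 15, 30, 45, 60 and 75. Every interval is 15 days and 15 − 15 = 0.
- Concomitant doses fall on days 15, 45 and 75. Every interval is 30 days and 30 − 30 = 0. The time from Visit 1 to Visit 2 is covered because the duty starts at randomization.

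So no time before a remaining dose is uncovered in either group.

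**Largest single gap within the visit windows.**
- Staggered, Visit 1 to 2: 21 − 15 = 6 days.
- Staggered, later intervals: Visit 3 may be at day 42 with Visit 2 at day 15, an interval of 27 days, and 27 − 15 = 12 days. The same pattern holds for each later pair.
- Concomitant, Visit 2 to 4 and Visit 4 to 6: 42 − 30 = 12 days.

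The 12-day staggered gaps cannot all occur in one infant. With Visit 2 at day 15 and Visit 3 at day 42, Visit 4 can be no later than 15 + 42 = 57 and no earlier than 42 + 15 = 57, so the next gap is 0.

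**Total from Visit 1 to Visit 6.**

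| Schedule | Staggered | Concomitant |
|---|---|---|
| As scheduled | 0 of 75 days | 0 of 75 days |
| Mid-window (Visit 6 at day 90) | 5 × 3 = 15 of 90 (17%) | 2 × 6 = 12 of 90 (13%) |
| Latest Visits 2, 4, 6 (days 21, 63, 105) | 105 − 5 × 15 = 30 of 105 (29%) | 2 × 12 = 24 of 105 (23%) |

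Enumerating the in-window staggered schedules gives the same maximum of 30 days, for example with doses on days 0, 21, 36, 63, 78 and 105 (gaps 6, 0, 12, 0, 12).

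**Beyond the visit windows.** If a concomitant dose slips to the 70-day maximum V260 interval, the gap is 70 − 30 = 40 days.

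**After dose 3.** Visit 8 is 30 to 42 days after Visit 6. Uncovered: 30 − 15 = 15 to 42 − 15 = 27 days (staggered), and 30 − 30 = 0 to 42 − 30 = 12 days (concomitant). No vaccination remains to be stopped by then, so this counts only if discontinuation includes leaving the study.

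**An in-window example.** A staggered infant has Visit 2 on day 15 and Visit 3 on day 40. A nonserious illness starts on day 33, 18 days after the Visit 2 dose, and vaccination is stopped at Visit 3. Section 8.4.1 does not require that AE to be reported.

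**The case against.** The best answer is that the plan works as scheduled. The windows restart with each dose and equal the minimum intervals, so an infant seen on the planned days has no uncovered time before a remaining dose. That stands, and it limits the point to late visits.

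Other text also favours capture. The Schedule of Activities reviews AEs at every visit. Section 10.3.4 has AE information recorded at each examination. Section 8.4.3 asks for nonserious AEs in randomized participants to be followed to outcome. Section 7.1 requires certain data on clinical events to be collected after an infant stops vaccination. Reasons for discontinuation are displayed under Section 9.6.3. These make loss less likely, but none creates the missing duty:
- Review at visits is a procedure; Section 8.4.1 sets what must be reported.
- The follow-up in Section 8.4.3 is framed as following an initial report.
- Section 7.1 concerns events after stopping, not the event that caused it.
- Section 8.1.9 covers AEs present at withdrawal from the study and refers back to Section 8.4.
- A disposition reason carries no onset, grade or causality.

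Some stronger readings are not supported. A reader might infer that such AEs are not reported and that the endpoint is under-counted; Table 2 only says that reporting is not required, and the data entry guidelines it points to are not in these documents. A reader might assume that illness which stops vaccination tends to surface at the next dose visit; nothing in the documents says so. A reader might also put the concomitant share at 24 of 84 days (29%) by starting at Visit 2. Section 8.4.1 covers Visit 1 to Visit 2 in that group, so on the same Visit 1 to 6 basis it is 24 of 105 (23%). Finally, the different cut-offs by arm do not produce unequal planned coverage before dose 3: on schedule both groups have none uncovered.

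**Conclusion.** The mismatch is real and minor. The stated period of the endpoint is wider than the required collection of nonserious AEs, and no clause makes an AE that leads to discontinuation reportable at any time. The endpoint may therefore be incomplete when visits run late: by 0 days on schedule, and by at most 30 of 105 days (staggered) or 24 of 105 days (concomitant) within the visit windows.

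These shares are days at risk at the extreme dates. Reading them as shares of events would assume a constant onset rate and that every infant is seen at the latest date. The plan gives no event rate, so no under-count can be computed.

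The documents do not say whether discontinuation means stopping vaccination or leaving the study. Under the second meaning there is a further gap after dose 3 of 15 to 27 days (staggered) against 0 to 12 days (concomitant), present even on schedule in the staggered group and unequal between groups.

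The endpoint is reported as counts and percentages without a test or confidence interval, and the primary non-inferiority analysis is unaffected.

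**What to change.** In Section 8.4.1 and Table 2, state that any AE, serious or not, that leads to discontinuation of either study vaccine or to withdrawal from the study is reported whatever its onset day, in both groups. In Section 9.4.2 and Table 5, define discontinuation (which vaccine, or the study).

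Alternatively, leave collection as it is and restrict the stated period of the endpoint to the collection windows. The label would then match the data, but events that start between windows would stay outside the summary.

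The first option costs one sentence, one table entry and a few extra AE forms. Neither option changes when or why vaccination is stopped.
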